6.2.5 Completion/Final Evaluation

A participant will be considered to have completed the study following the completion of the 12-month follow-up, or the determination that the participant has been “lost to follow-up”. For the RCT, participants will be considered lost to follow-up following NCCIH guidelines. Specifically, for this trial, a participant will be considered lost to follow-up according to the following guidelines:

- (1) A participant does not complete three consecutive study follow-up assessments and is unresponsive to study contact. “Unresponsive to study contact” will be defined as the inability of research staff to receive any response initiated from the participant by contact either (a) in-person (at an assessment or home visit), (b) through the telephone (e.g. phone calls), (c) through project correspondence (mail, e-mail, or text message) or (d) through completion of online follow-up surveys for a consecutive 6 months of study participation. Due to the nature of the study population (participants experiencing chronic pain and opioid use disorders) and the design of the study, it is expected that schedule deviations may occur over the course of a participant’s enrollment in the study (e.g. participants may miss a scheduled study visit or therapy session). We will not consider these incidents of minor protocol deviations to be “lost to follow-up” until the participant has become unresponsive according to the above definition.
- (2) A participant is no longer participating in study activities. For this project, this can occur by:
 - (a) a participant requesting to withdraw their participation from the study, either by verbally communicating this information to a research staff member or through written communication (e.g. e-mail, mail, or text message) from the participant received by a research staff member. Once this request has been received, the participant will no longer be contacted by study staff and their participation in the study will be considered complete. Participant data collected prior to the participant’s decision to withdraw from the study will be used in data analyses unless the participant has specifically requested their data be removed; or
 - (b) a participant timing out of the study completion window. For this project, participants will be able to complete the final 12-month study

assessment from the assessment due date up until 3 months following that date. For example, if a participant is due to complete their 12-month follow-up on March 1, 2020 they will be eligible to complete that follow-up until June 1, 2020. On June 2, 2020 the participant will be outside of the study completion window and their participation will be considered complete.

Research staff may choose to end any treatment condition session or study assessment visit at any time if they believe (1) it is not in the best interest of the participant to continue (e.g. the participant becomes upset and/or is unable to continue, medical emergency, etc.) or (2) if staff believe their safety is at risk. Study staff will be trained in safety procedures to ensure their own safety when conducting study assessment visits. The same crisis reporting procedures for staff safety concerns will apply in terms of immediately contacting Drs. [name] or [name], or a clinical supervisor or project manager on call. As part of the follow-up assessment protocol, written safety procedures for conducting community-based follow-ups include meeting at public locations, during daylight hours, in pairs, and with mandatory call-in procedures. Prior research conducted by the study team using such procedures with similar populations has resulted in minimal incidents where staff safety concerns became an issue during follow-up assessments. All safety concerns regarding follow-up assessments will be reported immediately to Drs. [name] and [name]. Individual study participation may also be ended by PI discretion. Reasons for involuntary study withdrawal will be included in the informed consent document and may include:

- It is not in the best interest or is harmful to the participant to stay in the study.
- The researcher believes the individual's participation is harmful to others or staff.
- A participant becomes ineligible to participate (e.g. no longer can provide voluntary consent, changes in competency, etc).
- A participant does not follow instructions from the researchers (e.g. does not complete any of the study sessions or is determined to be "lost to follow-up").
- The study is suspended or canceled.
- Other administrative reasons or unanticipated circumstances.

Once a participant has completed all study requirements, research staff will have no further contact with participants for this study. They may, however, be contacted again if they provide consent to be contacted for future research studies (e.g. contacted for qualitative interviews). Adverse events or unexpected outcomes (e.g. participant hospitalization or deaths) will not be monitored or reported once a participant has completed the final 12-month follow-up assessment study visit.

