5.4 Adherence Assessment

For this study, adherence to the study intervention condition (PPMI) will be defined as participation in at least 50% of the condition sessions. This would equate to participating in at least 4 of the 8 study sessions. The PPMI condition is designed to be progressive in nature, with each

session building on materials learned or discussed during previous sessions. Because of this, receiving at least 4 sessions of material in the PPMI condition related to chronic pain management and buprenorphine adherence/retention, will be considered an adequate dose. Likewise, adherence to the study control condition (EUC) will also be defined as participation in at least 50% of the condition sessions, or 1 of 2 study sessions. Due to the nature of the study (a behavioral therapy intervention study), participants will not be required to attend study sessions and will not be compensated for their involvement in the individual sessions. Study therapists and research staff will discuss the benefits of remaining engaged in the study treatment during the initial study meeting, however participants will be free to discontinue the study sessions at any time. Study therapists will make reasonable attempts to contact the participant should they disengage from the sessions. Participants will only be allowed to complete study sessions up to 6 weeks post enrollment. This cutoff was determined to allow for adequate time for the participant to complete the 1-month follow-up assessment. Participants will be eligible to participate in all follow-up assessments regardless of study session participation.

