Participants will be considered in the study following enrollment and randomization until the completion of the 12-month follow-up or end of the 12-month follow-up window, whichever comes first. Participants will have a total of 6 weeks to complete all study treatment condition sessions. Ideally, condition sessions will be completed by Week 5 of study participation to allow for the timely collection of 1-month data. 1-, 3-, 6-, 9-, and 12-month follow-up data may be collected from the follow-up visit due date \pm 12 weeks (3-months).

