Participants may decide to discontinue their participation for any reason, at any time. Any participant requesting to withdraw their participation from the study, either by verbally communicating this information to a research staff member or through written communication (e.g. e-mail, mail, or text message) will no longer be contacted by study staff and their participation in the study will be considered complete. Participant data collected prior to the participant's decision to withdraw from the study will be used in data analyses unless the participant has specifically requested their data be removed. Participants may choose to discontinue participation in the intervention portion of the study (e.g. PPMI or EUC sessions) and will remain active in the study and continued to be followed with their permission. Research staff may choose to end any assessment or condition session early, using clinical discretion, if (1) they believe it is in the best interest of the participant (e.g. the participant becomes upset and/or is unable to continue, medical emergency, etc.), or (2) if staff believe their safety is at risk. As noted above, individual study participation may also be ended by PIs discretion. Reasons for involuntary study withdrawal will be included in the informed consent document and may include: (1) if it is not in the best interest or is harmful to the participant to stay in the study; (2) if the researcher believes the individual's participation is harmful to others or staff; (3) the participant becomes ineligible to participate (e.g. no longer can provide voluntary consent, changes in competency, etc); (4) the participant does not follow instructions from the researchers (e.g. does not complete any of the study sessions or is determined to be "lost to follow-up"); (5) the study is suspended or canceled; or (6) other administrative reasons or unanticipated circumstances.

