9.3 Definition of Populations

For this study, analysis will use an intent-to-treat (ITT) framework, where participants are classified by the condition they were randomized to, regardless of what they received. Cox Proportional Hazards regression models will be used to test the association between group assignment and time to dropping out of buprenorphine treatment. We will test whether the assumptions for this modeling technique are met, and if they are not, consider variable transformations or alternative modeling strategies (e.g., generalized linear models).

While primary analyses will use the ITT framework, we will further examine treatment effects by conducting a per-protocol analysis. As stated earlier (see Section 5.4 "Adherence Assessment"), participants will be considered to be "per-protocol" if they complete at least 4 sessions of the PPMI condition, or 1 session of the EUC condition. This cutoff equates to receiving 50% of the proposed material which will be sufficient to consider the intervention condition being received by the participant. Prior to conducting this analysis, we will verify the assumption that this cut-off represents a level of treatment compliance for participants (as intended by the study design) by comparing the associations of patient characteristics with the likelihood of attending six or more sessions. If this assumption is not met, we will consider alternative methods for comparing condition groups, such as complier average causal effect models, which use latent variable/training data methods to assign compliance levels for EUC group participants.

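### The plan lets the principal investigators end participation for attending no sessions, against its own rule that follow-up does not depend on attendance

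*Combined protocol and SAP*

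**What the plan says.** Section 6.2.5 opens its list of involuntary withdrawals with "Individual study participation may also be ended by PI discretion". One listed reason reads "A participant does not follow instructions from the researchers (e.g. does not complete any of the study sessions or is determined to be"; its second example is loss to follow-up. Section 8 repeats it: "the participant does not follow instructions from the researchers (e.g. does not complete any of the study sessions", again with lost to follow-up as the second example. Section 6.2.5 adds that these reasons go into the consent document.

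Other parts of the plan point the other way:

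- Section 5.4 says that attendance is not required, and then: "Participants will be eligible to participate in all follow-up assessments regardless of study session participation".
- Section 5.3.2 says that no intervention is required of participants.
- Section 8, in the same paragraph as the withdrawal list, says that people who stop PPMI or EUC sessions "will remain active in the study and continued to be followed with their permission".

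For the analysis, Section 9.3 defines intent-to-treat so that "participants are classified by the condition they were randomized to, regardless of what they received". Section 6.2.2 includes everyone enrolled in the analyses.

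**The concern.** For a participant who never attends a session, staff have two instructions that cannot both be followed: keep following the person, or end the person's participation. The consent form would carry the second.

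The choice matters because attendance is observed only after randomisation. The arms ask for very different effort: eight sessions of about 60 minutes in PPMI against two of 5-10 minutes in EUC (Section 5.1). A difference in zero-session rates is therefore plausible. The PIs hold the discretion, and they also review adherence data monthly (Section 9.2.1). Section 6.2.3 blinds follow-up data collectors, outcome adjudicators and analysts, but says nothing about whoever decides a withdrawal.

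If the discretion were used, outcomes would go missing, or be filled by assumption, in a selected group that may be unequal between arms. That is the kind of loss that intent-to-treat follow-up is meant to prevent.

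**Working it through.** **1. Can the rule reach the primary outcome?** Sessions may be completed only up to 6 weeks after enrolment (Sections 5.1 and 5.4), so zero-session status is final at week 6. The primary period runs to 3 months, with weekly surveys to week 13, and Section 9.5.1 makes the TLFB interview the main measure. A withdrawal at week 6 would lose the remaining weekly surveys, the 3-month TLFB and every assessment from 6 to 12 months. The documents do not say outright that data collection stops after a PI withdrawal, but that is the natural meaning of ending study participation.

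**2. How would such a person be coded?** Section 4 says only that the team may assume that people lost to follow-up are non-adherent. No rule is given for PI-withdrawn participants in the Cox model, so both censoring and counting as an event are open.

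**3. The plan's power figure.** Inputs from Section 9.2: 100 per arm, EUC event rate 50%, hazard ratio (HR) 0.5, two-sided alpha 0.05.

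- PPMI event rate: 1 − 0.5^0.5 = 29.3%. Expected events: 50 + 29.3 = 79.3.
- Schoenfeld: √(79.3 × 0.25) × ln 2 − 1.96 = 3.09 − 1.96 = 1.13, so power is 87.0%.
- Freedman: √79.3 × (0.5/1.5) − 1.96 = 1.01, so power is 84.3%.

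The stated figure of more than 85% reproduces with Schoenfeld's formula. It assumes all 200 are followed or inferred, so keeping non-attenders in follow-up leaves it unchanged.

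**4. What using the rule could do.** The documents give no zero-session rates, so all rates here are assumptions. Simulation: 100 per arm, exponential times over 13 weeks, EUC event rate 50%, log-rank test, 4,000 runs. Zero-session participants have the EUC hazard. Every one who is event-free at week 6 is withdrawn then, and either counted as an event or censored.

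A hand check for no true effect at 20% (PPMI) versus 5% (EUC), events counted: half of the zero-session group would have stayed event-free, so PPMI gains 20 × 0.5 = 10 false events and EUC gains 5 × 0.5 = 2.5. That makes 60 against 52.5 events where full follow-up gives 50 against 50.

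| True HR in attenders | Zero-session PPMI / EUC | Full follow-up: HR, rejection | Withdrawn, event: HR, rejection | Withdrawn, censored: HR, rejection |
|---|---|---|---|---|
| 1 | 5% / 5% | 0.999, 5.0% | 1.003, 4.9% | 0.993, 4.9% |
| 1 | 10% / 5% | 1.001, 4.8% | 1.074, 6.3% | 0.998, 4.8% |
| 1 | 20% / 10% | 0.997, 4.5% | 1.141, 10.5% | 1.001, 5.4% |
| 1 | 20% / 5% | 1.005, 5.4% | 1.222, 18.7% | 1.002, 5.0% |
| 1 | 5% / 10% | 1.006, 5.2% | 0.932, 6.0% | 1.001, 5.2% |
| 0.5 | 10% / 5% | 0.548, 77.4% | 0.608, 63.9% | 0.528, 80.0% |
| 0.5 | 20% / 5% | 0.588, 67.4% | 0.761, 26.2% | 0.555, 73.5% |
| 0.5 | 5% / 10% | 0.524, 82.4% | 0.497, 90.0% | 0.512, 82.2% |

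In the HR 0.5 rows, full follow-up gives more than 0.5 because non-attenders in PPMI are assumed to get no benefit. That diluted value is the intent-to-treat effect.

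**5. Sensitivity to assumptions.** A second simulation fixed the overall event rates (50% versus 29.3% for HR 0.5, 50% in both arms for the null) and gave non-attenders a 70% or 80% event rate. At 15% versus 5%, with the 70% rate, HR was 0.50 with full follow-up, 0.45 censored and 0.57 with events counted; power was about 84%, 90% and 70%. For the null at 20% versus 5% with events counted, it gave HR 1.14 and about 10% rejection, against 1.22 and 18.7% above. The assumptions drive the size.

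**The case against.** The strongest defence is that this is a stray example in a permissive list. Withdrawal is at the PIs' discretion, and nothing schedules a removal at week 6. Other text plainly expects non-attenders to stay: Section 5.1 defines a category for people who completed no sessions, Section 6.2.5 treats a missed therapy session as an expected schedule deviation, and Section 9.6 analyses by randomised condition irrespective of attendance.

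The arm difference is also inferred. One session avoids the trigger in either arm, PPMI offers eight chances to attend one, and both arms receive the same $40 after the first session. The nearest attendance figure is a mean of 8.9 of 10 telephone sessions in a different population, VA patients with chronic pain (Section 2.2). If a share z attended none, the mean could not exceed 10 × (1 − z), so z was at most 11% there. That is below the 15% and 20% used in the larger illustrations.

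All of this stands as a limit on size and likelihood. It does not remove the contradiction. The rule is written in two sections and sent to the consent form, and nothing says which instruction governs. That the rest of the plan expects non-attenders to stay is the reason to delete the example.

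A reader might also infer that the rule undercuts the Section 4 statement of primary-outcome data on 100% of those randomised. It does not: that statement rests on assuming that lost participants are non-adherent, not on interviewing everyone.

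**Conclusion.** The contradiction over zero-session participants is real and should be removed. Using the discretion could lose primary data after week 6 and all later outcomes in a group defined after randomisation. The secondary self-reported outcomes would be exposed too, with no coding assumption to fall back on.

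Size and direction are not known. They depend on the zero-session rate in each arm, on how often the PIs act, and on the coding. With a true benefit and more non-attenders in PPMI, counting events dilutes the effect and censoring overstates it, relative to full follow-up. If EUC had more non-attenders, counting events would favour PPMI. Equal rates give no distortion under the null.

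Three stronger readings are tempting and unsupported:

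- **That intent-to-treat is broken.** Participants stay in the analysis by randomised arm (Sections 6.2.2, 9.3 and 9.6). What is at risk is complete follow-up of those arms.
- **That the lost-to-follow-up example is equally at fault.** Section 6.2.5 defines it by three consecutive missed assessments with six months of no response. That does not depend on sessions, and the earliest run is months 1, 3 and 6, so it cannot normally arise before the 3-month endpoint.
- **That the sample size is wrong.** The power figure reproduces and is unaffected.

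**What to change.** 1. In Sections 6.2.5 and 8, and in the matching consent wording, delete completing none of the study sessions as a reason for involuntary withdrawal.
2. Add one sentence in both places: never starting sessions, or stopping them, ends sessions only, and the weekly surveys and the 1- to 12-month assessments continue with the participant's permission. This is needed because the general reason of not following instructions would otherwise still cover non-attendance.
3. In Section 9.6, fix in advance one rule for how anyone withdrawn by the PIs for other reasons enters the Cox analysis (censored or counted as an event, and at what date), in place of the optional assumption in Section 4.
4. Leave the safety, consent and capacity reasons and the Section 6.2.5 definition of lost to follow-up as they are.

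The cost is a wording amendment to the protocol and consent form, with the usual IRB approval, and some continued contact attempts using the tracking procedures already described in Section 6.2.4. Sample size does not change.

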7. SAFETY ASSESSMENTS

Once a participant has been enrolled in the study, their safety will be monitored throughout their duration on study in a variety of ways. As lead PIs, Drs. [name] and [name] will have the ultimate responsibility for monitoring the overall safety of the participants in the study, determining whether an event is considered an adverse event (AE) or serious adverse event (SAE), and reporting events as needed to the appropriate committees and agencies. Local site study personnel will be expected to notify the lead PIs, Project Managers, or other designated coordinating center personnel of serious

adverse events, noncompliance, or other study related problems as soon as they are identified. In all instances where participant safety is a concern, the participant will be evaluated and connected with the appropriate level of treatment services necessary. Senior clinicians are always on call for consultation if a participant seems distressed or needs special attention. All participants are instructed on how to obtain emergency care, should that be required. As a requirement of the NCCIH, this study will also include an Independent Monitoring Committee (IMC) or other study monitor which may perform oversight functions and report their observations and findings to the IRB or designated official as needed. Functions could include: observing recruitment and enrollment procedures and the consent process for individuals, overseeing study interventions and interactions, reviewing monitoring plans, or overseeing data matching, data collection, and analysis. These monitors may discuss the research protocol with the investigators, interview human subjects, and consult with others outside of the study about the research. The IMC or any other monitoring entity will have authority to stop a research protocol in progress, remove individual subjects from a research protocol, and take whatever steps are necessary to protect the safety and well-being of human subjects. Any patient safety events will be documented and reported to the appropriate entities (e.g. IRB, NCCIH, IMC, etc.) based on the study reporting requirements outlined below (see Section 7.4 “Reporting Requirements”) and the Data and Safety Monitoring Plan (DSMP) for this study.

Given the characteristics of the study population (participants with OUD experiencing chronic pain on buprenorphine treatment), we anticipate there may be **expected** adverse events that participants may experience while on study in the following domains:

(1) **Acute Opioid Risk Situations**, where subjects may mention or endorse opioid use habits that acutely increase their risk of an overdose.

A brief risk assessment will be completed if the participant endorses or reports experiencing an overdose within the past 30 days and/or use of their buprenorphine in addition to the use of opioids or other medications in a way that would lead to acute overdose risk; including other substances that, if they were to take when they left, have a high likelihood of experiencing an overdose. This includes, but is not limited to: probable use of heroin, cocaine, benzodiazepines, prescription opioids or snorting or injecting their medication if it is not written as such. Specific procedures for identifying and responding to this type of risk are included below (see section 7.2 “Methods and Timing for Assessing, Recording, and Analyzing Safety Parameters”) and in the study Data and Safety Monitoring Plan (DSMP). The research staff member will follow the Opioid Risk Assessment Protocol developed for this study and consult with the PIs to determine whether the participant’s distress was significant enough to warrant reporting such as an AE.

(2) **Breach of confidentiality** associated with data collection and necessary reporting of increased participant risk (suicide risk, homicide risk, or risk based on increased substance use) to appropriate authorities or health personnel.

There is a minor potential risk to confidentiality of assessment data and audio-recorded sessions. The risk of a violation of confidentiality exists because human participants will be disclosing personal information, both in assessments and therapy condition sessions. This risk is related to the damage that could be caused by an inadvertent release of sensitive information (e.g., psychiatric symptoms, substance use, etc.). Our research team has considerable experience in delivering study assessments in community locations while maintaining participant privacy as well as in maintaining the confidentiality of study data

and research records. Staff will have procedures in place to ensure data confidentiality (See Section 11.3 “Participant Confidentiality” for more details).

(3) **Homicidal ideation** as indicated by verbal report of thoughts of hurting others.

While the study does not directly ask about homicidal ideation, this information may be provided by the participant during an interaction with study team members. The protocol for handling homicidal ideation will be similar to that for suicidal ideation (see Section 7.2 “Methods and Timing for Assessing, Recording, and Analyzing Safety Parameters”). Specifically, if the participant articulates thoughts of hurting others, the study team member will ask the participant to elaborate on his/her thoughts/behaviors (e.g., is there an identified victim, does the participant have a plan). The level of action necessary will be based on the participant’s responses and whether the study team member perceives that the patient or someone else is in immediate danger. Study personnel will follow established safety protocols and contact local licensed clinical staff when appropriate.

(4) **Hospitalization or Emergency Department/Urgent Care visits** as a result of mental health or substance use (e.g. acute intoxication, acute withdrawal, suicide attempts).

(5) **Severe Emotional Distress** as indicated by:

- a. patient verbal report of a significant increase in psychiatric symptoms;
- b. patients reporting significant distress due to the content of the self-report measures;
- c. patients reporting significant distress due to the content of the PPMI or EUC conditions.

In each case, the research personnel will consult with the PIs to determine whether the participant’s distress was significant enough to warrant reporting as an AE.

(6) **Suicidal ideation** as indicated by:

- a. self-report of significant suicidal ideations and behaviors on pertinent study questionnaires (e.g. a non-zero response on item #9 of the Patient Health Questionnaire (PHQ-9) or the response “on purpose, I wanted to die” or “I didn’t want to die but I didn’t care about the risks either” on item #7 within Overdose History after indicating an overdose in the past 30 days (item #3).
- b. endorsement of recent suicidal thoughts, plans, or actions during the interview or assessment;
- c. endorsement of thoughts of suicide or suicidal behaviors during the PPMI or EUC sessions.

In each case, the research personnel will follow the suicide risk assessment protocol (see section 7.2 “Methods and Timing for Assessing, Recording, and Analyzing Safety Parameters” and the study Data and Safety Monitoring Plan) and consult with the PIs to determine whether the participant’s distress was significant enough to warrant reporting as an AE.

(7) **Psychological discomfort** as a result of being asked personal questions, particularly during the assessments and sessions. Participants may also become anxious or upset during discussions of their thoughts about issues such as their mental health treatment that occur during the sessions.

Study staff will be trained to respond to this discomfort, including receiving extensive crisis training and proper ways to refer participants to appropriate resources (i.e., treatment center staff, authorities, etc.) as necessary. Additionally, to minimize this risk, all participants will be informed of their right to refuse to answer any question they do not wish to answer and of their right to withdraw from the study at any time. Participants will also be informed that they can take breaks. There is a small risk that the PPMI and EUC conditions might upset participants. EUC sessions will focus on providing beneficial educational materials and participants will have opportunities to express and discuss any distressing thoughts or emotions these materials produce. The PPMI condition will utilize a CBT-based intervention. CBT for pain management approaches have established efficacy to improve pain-related functioning and it has been the experience of the project's investigators that these approaches dramatically diminish risks to participants from the study's intervention. Study therapist delivering both conditions will be masters-level therapists and will receive regular supervision by the [name], who is a licensed psychologist, or other specified staff member/clinical supervisor. They will also receive intensive training in dealing with high risk patients.

Unexpected events are always possible in intervention research. Given the study population, it is possible that participants will report other serious psychiatric or medical symptoms not listed above. Research staff will be trained to monitor significant abnormal behavior and/or report that the participant perceives him/herself to be in imminent need of medical treatment. If it is determined that the participant requires immediate care, the research staff will contact local licensed clinical staff and coordinate appropriate services. We anticipate that there will be several triggers that will dictate when action may be required to protect patient safety. These may include the participant's expression of severe distress, suicidal or homicidal ideation, and/or other serious psychiatric or medical symptoms. Research staff will be required to review all self-report measures that may indicate an elevated risk for suicide or acute substance use risk before the participant leaves the assessment or concludes a study session. All research staff will be extensively trained and adequately prepared for situations in which a participant may express severe distress, dangerous substance use, and/or suicidal ideation. Subsequent to any participant's expression of severe distress, ideation, or other serious symptoms, project staff will make all reasonable attempts to re-contact the participant to monitor his or her well-being until the acute situation is resolved.

For those who report suicidal ideation, determination of high risk for suicidality will be based on a combination of the information gathered during the assessments or condition sessions (both self-report and verbal interview) and the interaction between the research personnel and the participant. All research staff will be trained extensively to respond to emotional distress and to discuss concerns and issues should they arise. All staff will be trained in the study specific risk management protocol, which will resemble a modified version of the VA/DOD Clinical Practice Guideline for Assessment and Management of Patients at Risk for Suicide. Our group has extensive experience with suicide risk management and have drafted detailed protocols for these situations (a copy of the risk assessment flowchart is included in the Appendix of this protocol for reference). More broadly, study staff will be trained to perform attentive and empathic listening as well as exhibit calmness during all participant interactions. If the participant articulates thoughts of death or suicidal ideation, the research team member will ask the participant to elaborate on recent suicidal thoughts/behavior, if the patient has not already provided adequate information to judge risk level. The level of risk will be based on the participant's responses and whether the research team member perceives that the patient is in immediate danger (e.g., an active plan with intent to act

verbalized). Any determination of risk level above moderate risk must be confirmed by the licensed clinical staff member on call. Study personnel will follow established safety and risk assessment protocols and contact local licensed clinical staff when appropriate. Participants who are determined to be at an elevated risk for suicide will be supported in a variety of ways depending on the participant's need, including but not limited to (1) referred to their treatment provider, (2) directly connecting suicidal participants to the 24-hour suicide crisis hotline, proper authority, or emergency psychiatric services, or (3) arranging with local psychiatry crisis management staff to assess and potentially hospitalize the patient as necessary according to the study protocol. Ongoing follow-up will occur until it is determined that risk is minimal. If disclosure is required for safety, participants will be encouraged to disclose suicidal ideation to their healthcare provider prior to breaking confidentiality. Participants will be notified prior to breaking confidentiality that research staff must disclose what was discussed between research staff and the participant in regards to current suicidal thoughts or behaviors to ensure the participant's safety. The incident report will also include documentation that the discussion between the participant and the research staff about breaking confidentiality occurred. Thorough documentation of the situation and all actions taken by research staff or other applicable treatment providers involved will be submitted for review by the research staff member to the project managers and PIs.

The following procedures will be used to address **online-survey** responses that indicate potential suicide risk:

- (1) We will have an additional screen/page pop up for any participant who flags for suicide risk (e.g. endorses anything other than "not at all" on the PHQ item #9 asking about "thoughts that you would be better off dead, or of hurting yourself in some way" and/or endorses an overdose in the past 30 days on overdose history item #3 and indicates on item #7 the overdose was "on purpose, I wanted to die" or "I didn't want to die, but didn't care about the risks). The page will contain contact information for national and international suicide hotlines and web links to crisis centers. We will also include the study telephone number for non-emergencies. The URLs in the page open in a different window so the survey is not interrupted. These resources (and the health brochure) may be included in our study correspondence (i.e., letter, e-mail) regardless of risk level.
- (2) The page will stay open for a minimum time period in attempts to assure the participant has read the information. The participant will not be able to close out of the survey until they check a box that indicates they have read and understand the information presented to them. This will confirm that the participant has viewed the information.
- (3) REDCap will auto generate an email to the study team indicating "flagged" cases after the survey has been submitted. The email will have only the study ID.
- (4) At least three attempts will be made to reach the participant by phone within 72 hours to further assess level of risk and/or answer questions. If the participant does not respond to research staff contacts attempts, the PIs will determine the appropriate course of action needed based on the risk level and situation.

Surveys completed via **postal mail** (we expect that this will be a very rare occurrence) may include the resource brochure which includes national suicide hotlines and mental health services. Surveys that are returned in which the participant endorses anything other than "not at all" for PHQ item #9 asking about "thoughts that you would be better off dead, or of hurting yourself in some way", endorses an overdose in the past 30 days, item #3 of the overdose history questions, and

indicates on item #7 “on purpose, I wanted to die” or “I didn’t want to die, but didn’t care about the risk,” or that indicate suicidal ideation or harm to others will be contacted by study staff. Study staff will make at least three attempts to reach the participant by phone within 72 hours of receiving the survey to further assess level of risk and/or answer questions. If the participant does not respond to research staff contacts attempts, the PIs will determine the appropriate course of action needed based on the risk level and situation.

In addition to suicide risk, all research staff will also be trained and prepared for situations in which a participant not currently in treatment reports severe substance misuse, for example if the participant has recently experienced increased substance use plus an emergency substance-related situation requiring immediate medical care (e.g. overdose) within the past 30 days. Our protocol in this regard is based on previous research that developed and implemented human subjects’ protections termed “rescue treatment” or “protective transfer” in studies of people with substance use disorders receiving less than standard treatment or having a poor response to standard or experimental treatments. In our study, participants who report at follow-up (during an interview or self-report measure) that they were hospitalized or made an emergency room or acute care outpatient visit due to acute substance use within the past 30 days will be protected by having project staff conduct a brief risk assessment and provide them with a resource brochure with local substance abuse resources and/or a referral to substance abuse treatment. Participants who require rescue treatment or immediate medical attention will be referred to the hospital or treatment provider closest to where they are residing. If the nearest facility is rejected by the participant for any reason, project staff will utilize SAMHSA’s online substance abuse treatment facility locator to provide a list of appropriate services.

